### 2.6.5 Subgroup analyses

For each secondary endpoint, subgroup analyses will be performed utilizing the corresponding secondary analysis model (Section 2.6.1 to Section 2.6.3), after adding the fixed-effect factors of subgroup variable and subgroup-variable-by-treatment interaction into the original model. The following subgroup variables (Section 2.2.1, Table 2-3) will be used for the subgroup analyses for all secondary endpoints.

- Region
- Stratum (ACEi, ARB, No RASi)
- Age group (< 65 years, ≥ 65 years)
- Age group (< 75 years, ≥ 75 years)
- Sex
- Baseline NYHA class group

- Diabetes (history or HbA1c  $\geq$  6.5%)
- LVEF group ( $\leq$  60%,  $>$  60%)
- Prior heart failure hospitalization

For changes from baseline in KCCQ CSS, KCCQ OSS, SF-36 PCS score and SF-36 MCS score, based on the corresponding subgroup analysis model, the estimates and the two-sided 95% confidence intervals will be provided for the adjusted means for the change from baseline at Week 24 in both treatment groups (LCZ696 and IMT) within each subgroup, and for the adjusted mean difference (LCZ696 minus IMT) at Week 24 within each subgroup; the p-value for the subgroup-variable-by-interaction will be provided for each subgroup variable.

For NYHA class change, based on the corresponding subgroup analysis model, the estimates and the two-sided 95% confidence intervals will be provided for the adjusted odds ratios (LCZ696 / IMT) at Week 24 within each subgroup; the p-value for the subgroup-variable-by-interaction will be provided for each subgroup variable.

The FAS will be used for the above subgroup analyses.

## 2.7 Analysis of the exploratory objectives

### 2.7.1 NT-proBNP up to Week 24

Plasma NT-proBNP will be collected using central lab.

All post-screening NT-proBNP from central lab will remain blinded until data base lock. Only the NT-proBNP at screening will be reported to the investigator and the Novartis clinical study team.

For the NT-proBNP, if the test value is below the LLOQ, the test value will be imputed by  $0.5 \times$  LLOQ; if the test value is above the ULOQ, the test value will be imputed by  $1.5 \times$  ULOQ.

For the NT-proBNP, unreliable test values will be set to missing.

For patients who permanently discontinue study treatment, values collected after permanent discontinuation will generally be included in the analysis.

The changes from baseline in log(NT-proBNP) will be analyzed using a MMRM model, in which, the response variable will be the changes from baseline in log(NT-proBNP); stratum (ACEi, ARB, No RASi), region, treatment (LCZ696, IMT), visit and treatment-by-visit interaction will be included as fixed-effect factors; BLNTBNP, stratum-by-BLNTBNP and visit-by-BLNTBNP interactions will be included as covariates; the within-patient covariance will be modeled using an unstructured covariance matrix (a common matrix for the two treatment groups). If the model fitting procedure does not converge, the AR(1) covariance structure will be used. The analysis will include all post-baseline scheduled visits up to Week 24 (Week 4, Week 12 and Week 24) and will be performed based on the likelihood method with an assumption of MAR for missing data.

Based on the MMRM model, the estimates and the two-sided 95% confidence intervals will be provided for the adjusted geometric means for the ratio to baseline in NT-proBNP at each post-baseline scheduled visit (Week 4, Week 12 and Week 24) in both treatment groups (LCZ696 and IMT), and for the ratio of the adjusted geometric means (LCZ696/IMT) at each post-

baseline scheduled visit (Week 4, Week 12 and Week 24). The corresponding one-sided p-values will also be provided based on the MMRM model.

As an additional supportive analysis, the changes from baseline in log(NT-proBNP) will be analyzed using a MMRM model, in which, the response variable will be the changes from baseline in log(NT-proBNP); stratum (ACEi, ARB, No RASi), region, visit, treatment (LCZ696, IMT) and treatment-by-visit interaction will be included as fixed-effect factors; BLNTBNP, BSBP, stratum-by-BLNTBNP, stratum-by-BSBP and visit-by-BLNTBNP interactions will be included as covariates; the within-patient covariance will be modeled using an unstructured covariance matrix (a common matrix for the two treatment groups). If the model fitting procedure does not converge, the AR(1) covariance structure will be used. The analysis will include all post-baseline scheduled visits up to Week 24 (Week 4, Week 12 and Week 24) and will be performed based on the likelihood method with an assumption of MAR for missing data.

Based on the supportive MMRM model, the estimates and the two-sided 95% confidence intervals will be provided for the adjusted geometric means for the ratio to baseline in NT-proBNP at each post-baseline scheduled visit (Week 4, Week 12 and Week 24) in both treatment groups (LCZ696 and IMT), and for the ratio of the adjusted geometric means (LCZ696/IMT) at each post-baseline scheduled visit (Week 4, Week 12 and Week 24). The corresponding one-sided p-values will also be provided based on the MMRM model.

Besides, the NT-proBNP test values and NT-proBNP ratio to baseline will be summarized by treatment group and visit, for overall and for each stratum (ACEi, ARB, No RASi), using number of observations, mean, standard deviation, geometric mean, 95% confidence interval for geometric mean, median, minimum, Q1, Q3, maximum, number of observations below the LLOQ and number of observations above the ULOQ.

The FAS will be used for the above analyses.

### **2.7.2 Estimated glomerular filtration rate (eGFR)**

The eGFR will be evaluated by the central laboratory, but local laboratory assessments will be performed in addition to the required central laboratory.

Only the central laboratory assessments will be used in the following analyses.

For the rate change in eGFR, the eGFR slope will be estimated from a mixed model, in which, the response variable will be the eGFR; stratum (ACEi, ARB, No RASi), region, and treatment (LCZ696, IMT) will be included as fixed-effect factors; time (in month) and treatment-by-time interaction will be included as covariates; a patient level random intercept and a patient level random slope (time) will be included as random effects with a unstructured covariance matrix (a common matrix for the two treatment groups). Here, the time (in month) will be computed as (date of assessment minus date of randomization plus one day)/(30.4375 day/month). The analysis will include all assessments from central laboratory at all visits up to Week 24 (Baseline to Week 24, scheduled or unscheduled) and will be performed based on the likelihood method with an assumption of MAR for missing data.

Based on the mixed model, the estimates and the two-sided 95% confidence intervals will be provided for the adjusted mean slope in each of the two treatment groups (LCZ696 and IMT), and for the adjusted mean difference (LCZ696 minus IMT).

Besides, the eGFR test values and the change from baseline in eGFR will be summarized by treatment group and visit, separately, for overall and for each stratum (ACEi, ARB, No RASi), using number of observations, mean, standard deviation, median, minimum, Q1, Q3, and maximum. The summary will include all scheduled assessments.

The FAS will be used for the above analyses.

## 2.8 Safety analyses

The SAF will be used for all safety analyses.

### 2.8.1 Adverse events (AEs)

All AEs will be recorded on the CRF page “Adverse Events” and be identified using Medical Dictionary for Regulatory Activities (MedDRA). The MedDRA version used for reporting the study will be described in a footnote.

An AE with its severity increased should be considered and recorded as a new AE.

The missing or partially missing start/end date for AEs will be imputed based on the Novartis AGB global standards.

Treatment emergent adverse events (TEAEs) are defined as any recorded AE with its start date (recorded or imputed) later than or equal to the date of the first dose of the study drug.

Study drug related AEs are defined as any recorded AE with “Reasonable possibility that AE is related to study treatment” answered as “YES”.

AEs leading to permanent discontinuation of study treatment are defined as any recorded AE with “Action taken with study treatment” answered as “DRUG WITHDRAWN”.

AEs leading to dose adjustment or temporarily interruption of study treatment are defined as any recorded AE with “Action taken with study treatment” answered as “DOSE REDUCED”, “DOSE INCREASED” or “DRUG INTERRUPTED”.

Most common TEAEs are defined as any recorded TEAE corresponding to a PT with at least 2% of patients in either treatment group (LCZ696 or IMT) having at least one TEAE of this PT.

SAEs are defined as any recorded AE with “Does AE meet the definition of an SAE” answered as “Yes”.

The following rules are applicable to the summaries.

- If a patient reported more than one AE with the same PT, the patient will be counted only once with the greatest severity at the PT level
- If a patient reported more than one AE within the same SOC, the patient will be counted only once with the greatest severity at the SOC level, where applicable.

The following summaries will be performed.

- TEAEs will be summarized by treatment group, SOC and PT, and summarized by treatment group, SOC, PT and maximum severity, for overall and for each stratum (ACEi, ARB, No RASi).

- Study drug related TEAEs will be summarized by treatment group, SOC and PT, and summarized by treatment group, SOC, PT and maximum severity, for overall and for each stratum (ACEi, ARB, No RASi).
- TEAEs leading to permanent discontinuation of study treatment will be summarized by treatment group, SOC and PT, for overall and for each stratum (ACEi, ARB, No RASi).
- TEAEs leading to dose adjustment or temporarily interruption of study treatment will be summarized by treatment group, SOC and PT, for overall and for each stratum (ACEi, ARB, No RASi).
- Most common TEAEs will be summarized by treatment group, SOC and PT, for overall and for each stratum (ACEi, ARB, No RASi).
- Study drug related most common TEAEs will be summarized by treatment group, SOC and PT, for overall and for each stratum (ACEi, ARB, No RASi).
- Treatment emergent SAEs (TESAEs) will be summarized by treatment group, SOC and PT for overall and for each stratum (ACEi, ARB, No RASi).
- Most common TESAEs will be summarized by treatment group, SOC and PT, for overall and for each stratum (ACEi, ARB, No RASi).
- Study drug related TESAEs will be summarized by treatment group, SOC and PT, for overall and for each stratum (ACEi, ARB, No RASi).

The SAF will be used for the above analyses.

Table 2-9 shows the safety topics of interest for LCZ696 and the specifically specified analyses for each safety topic. In addition, the following standard analyses will be applied to all safety topics.

- Numbers and percentages of patients with any TEAE within the safety topic name (or PT within safety topic name) will be provided by treatment group, safety topic name, PT and maximum severity, for overall and for each stratum (ACEi, ARB, No RASi).
- Exposure adjusted incidence rates per 100 patient-years for TEAEs within the risk name will be provided by treatment group and safety topic name, for overall and for each stratum (ACEi, ARB, No RASi).
- Listing of patients numbers per safety topic.

The search paths for the related preferred terms (PTs), high level group term (HLGT), high level term (HLT), in Standard Medical Queries (SMQs), or NMQ in MedDRA for the safety topics in Table 2-9 are store in the LCZ696 Case Retrieval Strategy (2019).

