The use of an open-label ACEi, ARB or a renin inhibitor is prohibited while the patient is taking study drug. Should the patient receive open-label RASi or renin inhibitor during the study, study drug must be withdrawn and the patient continued to be followed within the study. Patients must wait 36 hours after last study drug administration prior to initiating open label ACEi. Whenever possible, as dictated by clinical status, patients should resume study drug. Study drug re-initiation should be at the dose level deemed appropriate by the investigator and up-titration to target dose undertaken as described above. Patients who received open label ACEi should wait 36 hours before resuming study medication. These changes must be recorded on the Dosage Administration Record eCRF.

In case of pregnancy discovered during the screening epoch, the patient will be excluded from the study. In case of pregnancy discovered during the randomization epoch, the patient should be instructed to immediately discontinue study drug and encouraged to continue to attend scheduled study visits.

See [Section 7.6](#) for further details on pregnancies and reporting guidelines.

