5.6 Study completion and discontinuation

5.6.1 Study completion and post-study treatment

A patient will be considered to have completed the study when the patient has completed the last visit planned in the protocol. The study will be completed when the last patient enrolled has completed their last visit (24 weeks after randomization). Patients will continue to be followed in the study regardless of study drug discontinuation.

The investigator must provide follow-up medical care for all patients who are prematurely withdrawn from study drug, or must refer them for appropriate ongoing care. An open-label extension study may be available through the sponsor dependent on the results of the PARAGON-HF study.

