## 2.2 Analysis sets

The following analysis sets will be used for the statistical analyses.

- **Screened set (SCR)** – All patients who signed the informed consent for CLCZ696D2302. The SCR includes only unique screened patients, i.e., in the case of re-screened patients only the chronologically last screening data is counted.

- **Randomized set (RAN)** – All patients in the SCR who received a randomization number, regardless of receiving study drug.
- **Full analysis set (FAS)** – All randomized patients with the exception of those patients who have not been qualified for randomization and have not received study drug, but have been inadvertently randomized into the study, and the exception of those patients who have been inadvertently randomized within a wrong stratum (ACEi, ARB, No RASi) and have not received study drug. Further exclusions from the FAS may only be justified in exceptional circumstances (e.g., *serious* GCP violations). Following the intent-to-treat principle, patients will be analyzed according to the treatment to which they were assigned at randomization. Efficacy variables will be analyzed based on the FAS as the primary set.
- **Per protocol set (PPS)** – A subset of the FAS which will consist of the patients who do not have major deviations from the protocol procedures in the randomized treatment epoch. Major protocol deviations will be pre-specified prior to unblinding treatment codes for analyses. This supplemental efficacy set will be used to support the primary analysis results.
- **Safety set (SAF)** – All randomized patients who received at least one dose of study drug. Patients will be analyzed according to the treatment actually received. The SAF will be used for the analyses of safety variables. The treatment actually received will be considered identical to the randomized treatment if the patient has received at least one dose of the randomized treatment.

Patients without valid written informed consent will be excluded from all analysis sets. Further exclusions from the FAS are only justified in exceptional circumstances (e.g., site closed down for GCP reasons). The determination of which patients were excluded from the FAS is made in a blinded manner before the database lock.

Rules leading to exclusion from the analysis sets are given in [Appendix 5.2](#).

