- For changes from baseline in 6MWD, for each post-baseline scheduled visit up to Week 24 (Week 16 and Week 24), the imputation model will be a linear regression model specified using fully conditional specifications, in which, the response variable will be the change from baseline in 6MWD at the visit; region will be included as a fixed-effect factor; B6MWD, BSBP, change from baseline in 6MWD at the closest previous post-baseline scheduled visit (not applicable for Week 16, Week 16 for Week 24) will be included as covariates. For each stratum (ACEi, ARB, No RASi) and each arm, the imputation model will be fitted separately based on the data from patients with B6MWD ranging from 100 meters to 450 meters in the arm within the stratum.

Furthermore, the missing data patterns in the change from baseline in the log(NT-proBNP) and the change from baseline in 6MWD will be explored via by-treatment-group box plots for patients who permanently discontinue from study treatment due to adverse events, death or lack of efficacy, for patients who permanently discontinue from study treatment due to any other reasons, for patients who did not permanently discontinue from study treatment, and for patients

who take open label LCZ696 after permanent discontinuation from study treatment. Similar box plots will also be provided for on-treatment assessments.

As additional supportive analyses, the primary analyses for the primary endpoints (change from baseline in log[NT-proBNP] at Week 12, and change from baseline in 6MWD at Week\_24) described in Section 2.5.2 will be performed for the following data as applicable.

- Data where the 6MWD after the death were set to missing for patients who died.
- Data where the last observation carry forward (LOCF) approach was performed for missing data.
- Data where the responses after the first dose of open-label RASi or open-label LCZ696 after permanent discontinuation of the study treatment will be set to missing and considered MAR. (This is called on-treatment analysis.)

The FAS will be used for the above analyses.

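### Treatment-emergent AEs have no cut-off tied to last dose and the patient-year denominator is unnamed, so the SAP yields no on-drug rate for its safety topics

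*SAP*

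**What the plan says.** **The event window.** SAP 2.8.1 counts as treatment-emergent "any recorded AE with its start date (recorded or imputed) later than or equal to the date of the first dose of the study drug". Neither document adds an upper limit relative to last dose.

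**Where it is used.** For the topics in SAP Table 2-9, which include angioedema, hyperkalemia, hypotension and renal impairment, "the following standard analyses will be applied to all safety topics". One of these analyses is the rate: "Exposure adjusted incidence rates per 100 patient-years for TEAEs within the risk name will be provided by treatment group". The SAP does not say which patient-years are meant.

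**Which arm an event belongs to.** SAP 2.2 fixes this early: "The treatment actually received will be considered identical to the randomized treatment if the patient has received at least one dose of the randomized treatment". A later change of drug does not move an event.

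**Follow-up off drug.** Protocol 5.6.1: "Patients will continue to be followed in the study regardless of study drug discontinuation". When open-label RASi is given, Protocol 5.5.5 states that "study drug must be withdrawn and the patient continued to be followed within the study"; study drug may be resumed later. Protocol 9.4.4 and SAP 2.5.4 also foresee open-label LCZ696 after permanent discontinuation.

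**When collection ends.** AEs are collected to the end-of-study visit (Protocol 7.1), and SAEs to 30 days after the last study visit (Protocol 7.2.2).

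**The efficacy counterpart.** SAP 2.5.4 has a supportive on-treatment analysis in which "responses after the first dose of open-label RASi or open-label LCZ696 after permanent discontinuation of the study treatment will be set to missing", and SAP 2.6.4 repeats it for secondary endpoints. Section 2.8 has no such analysis.

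**The concern.** Protocol 3.6 names hypotension, hyperkalemia, worsening renal function and angioedema as risks shared by LCZ696, enalapril and valsartan. A patient can therefore leave study drug, start an open-label drug carrying the same risks, and have the resulting event tabulated under the randomized arm. Two cases follow directly from the wording:

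- Angioedema in an IMT patient taking open-label LCZ696 is an IMT event.
- Hyperkalemia in a No RASi placebo patient taking an open-label ARB is a placebo event.

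A rate labelled exposure-adjusted is normally read as events per unit of time on drug. Here the numerator includes off-drug events, and the denominator is left open. A reader of the study report could not tell what the rate estimates, and could not recover an on-drug rate for the topics where attribution to drug matters most.

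**Working it through.** The documents state no AE rate, stopping rate or patient-year total, so there is no figure of the plan to reproduce. The check is of definitions, followed by an illustration on declared assumptions.

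**1. Candidate denominators, all from SAP 2.4.1**

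- Study drug exposure: days on dose levels 1 to 3.
- Duration of treatment: first to last dose, interruptions included.
- Study exposure: randomization to last visit.

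The first two set events from after permanent discontinuation over time that excludes that period. The third roughly matches the numerator but mixes on-drug and off-drug time. None gives an on-drug rate while the numerator stays as defined.

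**2. Size for a single arm**

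Let *d* be the share who stop for good, *s* the mean week of stopping, and *R* the off-drug event rate divided by the on-drug rate.

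- Off-drug share of patient-time: *f* = *d* × (24 − *s*)/24
- Reported rate ÷ on-drug rate, with on-drug time as denominator: 1 + *R* × *f*/(1 − *f*)
- The same, with time in study as denominator: (1 − *f*) + *R* × *f*

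Take *s* = 12 and *R* = 1 (assumed):

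- *d* = 10%: *f* = 0.10 × 12/24 = 0.05; factor 1/(1 − 0.05) = 1.05
- *d* = 20%: *f* = 0.20 × 12/24 = 0.10; factor 1/(1 − 0.10) = 1.11

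For 1250 patients per arm over 168 days (574.9 patient-years), 10% stopping at Week 12 puts 28.7 patient-years off drug.

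**3. Wider range**

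The on-drug rate is set at 10.0 per 100 patient-years, with stopping at Week 4 or 12 and *R* from 0.25 to 3, all assumed.

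| Share stopping | On-drug time as denominator | Time in study as denominator |
|---|---|---|
| 5% | 10.1 to 11.3 | 9.7 to 10.8 |
| 10% | 10.1 to 12.7 | 9.4 to 11.7 |
| 20% | 10.3 to 16.0 | 8.8 to 13.3 |

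With on-drug time the rate can only be inflated. With time in study it can be inflated or diluted.

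**4. Between arms**

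If both arms share the same *d*, *s* and *R*, the factor is the same in each and cancels in the rate ratio. If 20% stop in one arm and 10% in the other, with *s* = 12, *R* = 1 and on-drug time as denominator, the ratio shifts by (1/0.90)/(1/0.95) = 0.95/0.90 = 1.056, against the arm with more stopping. Nothing in the documents says which arm that would be, or how *R* would differ.

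**5. A check on the remedy**

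Suppose an on-treatment window of last dose plus 30 days were applied in full to completers. Each would contribute 168 + 30 = 198 days of denominator, but non-serious AEs are collected for only 168. The rate would be multiplied by 168/198 = 0.85, a dilution of up to 15%. The window must therefore also stop where AE collection stops.

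**The case against.** The main objection is that this is a request for another table, not an error. Patients are deliberately followed after stopping drug, counting their events by assigned arm is a legitimate treatment-policy summary, and Protocol 9.5.2 plans no formal inference on safety. That stands, and it is why the current tables should be kept.

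The plan also has safeguards:

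- SAP 2.8.1 tabulates drug-related events and those leading to dose adjustment, interruption or discontinuation, and lists patients by safety topic.
- SAP 2.4.2 tabulates open-label ACEi, ARB and sacubitril/valsartan use by arm and stratum.
- Angioedema reports go to adjudication (Protocol 6.5.7 and 8.5).

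These limit the harm, especially for rare angioedema. None of them is a cut by timing, and the exposure-adjusted rates are not restricted to any of these subsets.

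A reader might infer that the window never closes. The documents do not support that: collection ends at the end-of-study visit, or 30 days after the last visit for SAEs. What is missing is a limit tied to last dose. Nor do they support extending open-label LCZ696 to temporary interruptions, since it is foreseen only after permanent discontinuation. Open-label RASi can occur during either.

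**Conclusion.** The point holds as a gap in the safety summaries. The treatment-emergent definition yields a treatment-policy count, the rate built on it has no stated denominator, and no on-drug view accompanies it although efficacy has one. If the denominator is drug exposure or treatment duration, numerator and denominator do not match, and the single-arm rate is inflated by about 5% to 11%. That range rests on 10% to 20% stopping at a mean of Week 12 and equal event rates on and off drug, both assumed.

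A reader might infer that open-label use pulls the arms toward each other and so hides drug-specific harm. The documents do not show this. They give no rate of stopping or open-label use, and the counting rule is the same in both arms. Protocol 5.5.7 directs blood pressure elevations to non-RASi therapy, and an IMT patient in the ACEi or ARB stratum who moves to open-label RASi remains on RAS blockade. The effect on the comparison is uncertain in size and direction.

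This is a cheap improvement.

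**What to change.** In SAP 2.8.1:

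- **Keep the current tables** as the treatment-policy view, and name their patient-year denominator: time in study over the same window in which the events are collected.
- **Add a supportive on-treatment set** for the Table 2-9 topics, SAEs and exposure-adjusted rates. It counts AEs from first dose to the earliest of (a) last dose plus a pre-specified window, (b) first open-label RASi or LCZ696 dose, and (c) the end of AE collection, which is the end-of-study visit for non-serious AEs. Patient-years are counted over the identical interval.
- **State a rule for patients who resume study drug** after open-label use or an interruption.

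The cost is SAP text and one extra set of tables. Dosing intervals and open-label use are already recorded (SAP 2.4.1 and 2.4.2). The window length must be fixed before unblinding. Cutting at the open-label switch may be informative censoring, since a switch can follow poor tolerability, so the on-treatment set should be read beside the treatment-policy tables and not in their place.
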